7.3.6 Adverse Events of Special Interest

AEs of special interest are AEs the sponsor may wish to carefully monitor. These AEs may be serious or nonserious and should be reported on the electronic data source and the SAE worksheet. These AEs are not considered SAEs unless they meet the definition of an SAE.

AEs related to potential substance abuse and suicide (serious or nonserious) are considered to be of scientific and medical concern specific to ASP8062, for which ongoing monitoring and reporting is required.

Additional information around AEs of special interest will be collected to complete participant narratives. AEs of special interest related to potential substance abuse are listed in [Section 10.10 Appendix 10 Adverse Events of Interest Related to Potential Substance Abuse and Following Drug Withdrawal].

AEs of special interest with respect to morphine include respiratory depression, constipation, nausea, vomiting, sedation, somnolence, lightheadedness, dizziness, and sweating.

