9.4.3 Analysis of Safety

For analysis of safety, the treatment groups are (ASP8062 alone, placebo alone, morphine in combination with ASP8062, morphine in combination with placebo).

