9.4.3.1 Adverse Events

AEs will be coded using MedDRA. An AE with onset at any time from first dosing until last scheduled procedure will be classified as a treatment-emergent adverse event (TEAE) for inclusion in the summary tabulations. An IP-related TEAE is defined as any TEAE with a causal relationship assessed as “yes” by the investigator, or records where the relationship is missing.

An overview and separate summaries of the number and percentage of participants with TEAEs, IP-related TEAEs, TEAEs leading to withdrawal of treatment, IP-related TEAEs leading to withdrawal of treatment and TEAEs excluding SAEs that equal or exceed a threshold of 5% in any treatment group will be presented by SOC, preferred term and treatment group. Also included in the overview are the number and percentage of participants with serious TEAEs, IP-related serious TEAEs, TEAEs leading to death and IP-related TEAEs leading to death.

The number and percentage of participants who have a TEAE within the drug abuse dependence Standardized MedDRA Queries (SMQ) (MedDRA v22.0) as classified by SOC

and preferred term, will be summarized by treatment group. In addition, the number and percentage of participants who have drug abuse-related TEAEs as classified by preferred term and lowest level term will be summarized by treatment group [Section 10.10 Appendix 10 Adverse Events of Interest Related to Potential Substance Abuse and Following Drug Withdrawal].

The number and percentage of participants who have a TEAE with the drug withdrawal SMQ (MedDRA v22.0) as classified by SOC and preferred term will be summarized by treatment group. In addition, the number and percentages of participants who have withdrawal-related TEAEs as classified by SOC and preferred term will be summarized by treatment group [Section 10.10 Appendix 10 Adverse Events of Interest Related to Potential Substance Abuse and Following Drug Withdrawal].

AE data will be listed.

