49.	My movements are free, relaxed and pleasurable.			-1		

AMP: amphetamine; B: benzedrine; LSD: lysergic-acid-diethylamide; MB: morphine-benzedrine;
 PCA: pentobarbital-chlorpromazine-alcohol

10.10 Appendix 10: Adverse Events of Interest Related to Potential Substance Abuse and Following Drug Withdrawal

a. Includes Adverse Events of Interest Related to Potential Substance Abuse

Preferred Term	Lowest Level Term
Euphoria-related Terms	
Euphoric mood	Feeling high
	Euphoria
	Euphoric
	Euphoric mood
	Elevated mood
	Mood elevated
	Feeling abnormal
	Feeling drunk
	Feeling of relaxation
	Thinking abnormal
	Hallucination, mixed
Dizziness	Dizziness and giddiness
Dissociative/Psychotic Terms	
Psychosis	
Aggression	
Confusion	
Disorientation	
Terms Indicative of Impaired Attention, Cognition, Mood and Psychomotor Events	
Somnolence	Somnolence
Psychomotor hyperactivity/decreased activity	Hyperactivity/hypoactivity
	Mood disorders
	Mental impairment
	Drug tolerance, habituation, drug withdrawal syndrome, substance-related disorders
Inappropriate Affect	
Inappropriate affect	Elation inappropriate
	Exhilaration inappropriate
	Inappropriate mood elevation
Product tampering	Medication tampering

b. Related Adverse Events Occurring Following Drug Withdrawal

MedDRA v22.0 SOC	Higher Level Group Term	Higher Level Term	Preferred Term
Psychiatric disorders	Anxiety disorders and symptoms	Anxiety symptoms	Agitation
Nervous system disorders	Neurological disorders NEC	Neurological signs and symptoms NEC	
Psychiatric disorders	Depressed mood disorders and disturbances	Mood alterations with depressive symptoms	Anhedonia
Psychiatric disorders	Anxiety disorders and symptoms	Anxiety symptoms	Anxiety
Musculoskeletal and connective tissue disorders	Muscle disorders	Muscle related signs and symptoms NEC	Chills
Musculoskeletal and connective tissue disorders	Muscle disorders	Feeling and sensations NEC	
Psychiatric disorders	Depressed mood disorders and disturbances	Mood alterations with depressive symptoms	Depressed mood
Psychiatric disorders	Depressed mood disorders and disturbances	Depressive disorders	Depression
Gastrointestinal disorders	Gastrointestinal motility and defaecation conditions	Diarrhoea (excluding infective)	Diarrhoea
Psychiatric disorders	Mood disorders and disturbances	Emotional and mood disturbance NEC	Dysphoria
Nervous system disorders	Sleep disturbances (including subtypes)	Sleep disturbances NEC	Dyssomnia

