Psychiatric disorders	Sleep disorders and disturbances	Dyssomnias	
Psychiatric disorders	Depressed mood disorders and disturbances	Depressive disorders	Dysthymic disorder
Psychiatric disorders	Depressed mood disorders and disturbances	Mood alterations with depressive symptoms	Feeling of despair
Nervous system disorders	Headaches	Headaches NEC	Headache
Skin and subcutaneous tissue disorders	Skin appendage conditions	Apocrine and eccrine glad disorders	Hyperhidrosis
General disorders and administration site conditions	General system disorders NEC	General signs and symptoms NEC	
Psychiatric disorders	Sleep disorders and disturbances	Disturbances in initiating and maintaining sleep	Insomnia
Nervous system disorders	Sleep disturbances	Disturbances in initiating and maintaining sleep	
Psychiatric disorders	Depressed mood disorders and disturbances	Mood alterations with depressive symptoms	Morose
Gastrointestinal disorders	Gastrointestinal signs and symptoms	Nausea and vomiting symptoms	Nausea
Psychiatric disorders	Depressed mood disorders and disturbances	Mood alterations with depressive symptoms	Negative thoughts
Psychiatric disorders	Anxiety disorders and symptoms	Anxiety symptoms	Nervousness
Psychiatric disorders	Anxiety disorders and symptoms	Obsessive-compulsive disorders and symptoms	Obsessive thoughts

Table continued on next page

MedDRA v22.0 SOC	Higher Level Group Term	Higher Level Term	Preferred Term
General disorders and administration site conditions	General system disorders NEC	Pain and discomfort NEC	Pain
Nervous system disorders	Sleep disturbances (including subtypes)	Sleep disturbances NEC	Poor quality sleep
Psychiatric disorders	Sleep disorders and disturbances	Dyssomnias	
Cardiac disorders	Cardiac disorder signs and symptoms	Cardiac signs and symptoms NEC	Syncope
Vascular disorders	Decreased and nonspecific blood pressure disorders and shock	Circulatory collapse and shock	
Nervous system disorders	Neurological disorders NEC	Disturbances in consciousness NEC	Terminal insomnia (lower level term of interest: early morning awakening)
Psychiatric disorders	Sleep disorders and disturbances	Disturbances in initiating and maintaining sleep	
Nervous system disorders	Sleep disturbances	Disturbances in initiating and maintaining sleep	Tremor
Nervous system disorders	Movement disorders (including parkinsonism)	Tremor (excluding congenital)	
Gastrointestinal disorders	Gastrointestinal signs and symptoms	Nausea and vomiting symptoms	Vomiting

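### The withdrawal-related TEAE summaries have no off-drug onset window, so they cannot separate withdrawal from on-treatment events or acute day 10 morphine effects

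*Combined protocol and SAP*

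**What the plan says.** Section 9.4.3.1 sets one onset rule for all AE tabulations: "An AE with onset at any time from first dosing until last scheduled procedure will be classified as a treatment-emergent adverse event". Two withdrawal summaries follow. The first counts participants with a "TEAE with the drug withdrawal SMQ (MedDRA v22.0) as classified by SOC and preferred term will be summarized by treatment group". The second uses the sponsor's own term list: "withdrawal-related TEAEs as classified by SOC and preferred term will be summarized by treatment group". Neither adds an onset restriction.

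Section 9.4.3 fixes the columns: "the treatment groups are (ASP8062 alone, placebo alone, morphine in combination with ASP8062, morphine in combination with placebo". None of them is a post-treatment period.

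The sponsor's list is table b of Section 10.10 (Appendix 10), headed "Related Adverse Events Occurring Following Drug Withdrawal". It names no drug and gives no time window. Its terms include hyperhidrosis, headache, and nausea and vomiting (under the higher level term "Nausea and vomiting symptoms").

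Section 7.3.6 states: "AEs of special interest with respect to morphine include respiratory depression, constipation, nausea, vomiting, sedation, somnolence, lightheadedness, dizziness, and sweating". Section 4.1 gives ASP8062 or placebo on days 1 to 10, with morphine on day 10 straight after that day's ASP8062 or placebo dose.

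**The concern.** The heading of the term list describes a period after a drug is stopped, but the counting rule starts at the first dose. Because morphine is given directly after the last ASP8062 dose, its acute effects fall just where an off-drug period would begin. A plain rule of counting from the last dose would therefore not separate the two either.

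The tables also count participants, not events. A participant with nausea on day 10 and again on day 14 appears once under nausea, so the later episode adds nothing to the cell. A late difference between arms could be masked, and acute events could be read as withdrawal.

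**Working it through.** The plan states no figure for these tables, so there is nothing to reproduce. The check sets the rules side by side, then does simple arithmetic.

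**1. Onset window.** TEAEs run from day 1 to the last scheduled procedure. The end-of-study visit (ESV) is 5 to 9 days after the day 16 sample (Section 4.1):
- 16 + 5 = day 21; 16 + 9 = day 25.
- Dosing days as a share of the TEAE window: 10/21 = 48%; 10/25 = 40%.
- Days from the last dose to the ESV: 21 − 10 = 11; 25 − 10 = 15.
- In ASP8062 half-lives of about 60 h (Section 4.2): 11 × 24/60 = 4.4; 15 × 24/60 = 6.0.

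An off-drug period is therefore observed, but it is not tabulated separately.

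**2. Columns.** Section 9.4.3 gives no rule for assigning an AE to a column. The natural reading is that onset before the day 10 morphine dose goes to an alone column and later onset to a combination column. For completers, the ASP8062-alone column then covers days 1 to 9 and day 10 predose, all on treatment. The combination column holds both acute morphine effects and everything up to the ESV.

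**3. Term overlap.** Table b has 25 preferred terms as extracted. Three match morphine effects in Section 7.3.6: nausea, vomiting, and hyperhidrosis (sweating). Headache does not. The SMQ's terms are not reproduced in the documents. The missing onset limit applies to that table too, but its overlap with morphine effects cannot be checked here.

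**4. Illustration.** Section 9.2 plans about 24 participants, which is 16:8 at the 2:1 ratio. At least 18 are to complete, which is 12:6 if the ratio holds. Let p be the chance that a participant has at least one listed event caused by morphine on day 10. The documents give no value, so p is an assumption shown over a range. The expected count is n × p, and the chance of at least one is 1 − (1 − p)^n.

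| p (assumed) | ASP8062, n = 16: expected; chance of ≥ 1 | Placebo, n = 8: expected; chance of ≥ 1 |
|---|---|---|
| 10% | 1.6; 81% | 0.8; 57% |
| 25% | 4; 99% | 2; 90% |
| 50% | 8; > 99.9% | 4; 99.6% |

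With 12:6, the chances of at least one are 72% and 47% at p = 10%, and 97% and 82% at p = 25%. No withdrawal effect is assumed in any row, and the placebo participants have no ASP8062 to withdraw from.

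**5. A possible cut-off.** Table 2 takes the last morphine sample 48 h after the day 10 dose. Assuming log-linear decline at a 60 h half-life, the ASP8062 level at 48 h is 2^(−48/60) = 57% of its starting value. A window from 48 h to the ESV spans 11 − 2 = 9 to 15 − 2 = 13 days.

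**The case against.** A reader might infer that the plan reports morphine effects as ASP8062 withdrawal. The documents do not say that. Section 9.4.3.1 and Appendix 10 name no drug, no objective or endpoint in Table 3 concerns ASP8062 withdrawal, and Section 2.3.1 names only opioid withdrawal for monitoring. Nor can one say that the tables will mostly show morphine effects: three of 25 terms overlap, and the rates are assumed.

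The alone columns also have a use. Participants are recent opioid users who must test opiate-negative on day -1 and are then confined, so opioid withdrawal before day 10 is possible. Anyone stopping ASP8062 early stays in follow-up (Section 8.2), and off-drug events in such a participant would presumably fall in the ASP8062-alone column. These columns should stay.

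The strongest defence is the randomised control. Everyone dosed on day 10 receives morphine, so its acute effects appear in both combination columns. The study is descriptive, with no hypotheses or power calculation, and AEs are listed individually.

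All of this limits the harm but does not remove the problem. The control column has only about 6 to 8 participants. It cannot recover a late episode in someone already counted for the same term. Nor can it tell a withdrawal effect from a change in acute morphine tolerability caused by ASP8062, and tolerability of the combination is part of the primary objective. Listings hold the information but do not correct the summary.

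**Conclusion.** The point holds in a limited form. Followed exactly, the plan counts on-treatment events and acute day 10 morphine effects as withdrawal-related, so the table built on Appendix 10 table b cannot show what its heading describes. The SMQ table has the same onset gap.

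That conclusion rests on the text, plus the natural reading of how AEs are assigned to columns. The size depends on unknown rates: at 10% to 50%, between about 1 and 4 of 8 placebo participants would be counted with no withdrawal present. These are supplementary descriptive safety tables and no hypothesis test is affected. The change is still worth making before unblinding, because it uses data already collected.

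**What to change.** In Section 9.4.3.1, keep both planned four-column summaries and add a tabulation of withdrawal-related events by randomised arm (ASP8062 versus placebo), limited to AE episodes that start in a prespecified off-drug window ending at the ESV. Specify:

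- **Drug:** which drug's withdrawal is meant, ASP8062 or opioid.
- **Window start:** for example, after the 48 h post-day-10 sample, justified against the roughly 60 h ASP8062 half-life.
- **Early discontinuers:** anchor the window to the actual last dose.
- **Recurrence:** count a new episode even if the participant had the same term earlier.
- **Relisted events:** Section 7.3.1 relists an AE with a new onset date when its severity changes; do not treat that as a new onset.

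The cost is a few sentences, one extra table and some derivation logic, with no new data. The cut-off is a judgment, and events in the first 48 h would appear only in the planned tables.

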9.4.3.2 Laboratory Assessments

For quantitative clinical laboratory measurements (hematology and biochemistry), descriptive statistics will be used to summarize results and change from baseline by treatment group and time point.

The number and percentage of participants with potentially clinically significant values in liver enzymes and TBL will be tabulated.

Laboratory data will be listed.

9.4.3.3 Vital Signs

Descriptive statistics will be used to summarize vital sign results (blood pressure, pulse and respiratory rate) and changes from baseline for participants in the SAF by treatment group and time point.

The number and percentage of participants with respiratory rate values as per Table 7 at any time point will be summarized by treatment group. The lowest and highest respiratory rate, respectively, will be used in the analysis.

Table 7 Criteria for Respiratory Rate

Vital Sign	Criteria
Respiratory Rate (breaths/minute)	< 6, < 8, < 10 > 24, > 28, > 32, > 36

The number and percentage of participants who reach an alarm value for the continuous respiratory rate, and the number of times an alarm value was reached will be listed and summarized by treatment.

Vital signs data will be listed.

9.4.3.4 Continuous Pulse Oximetry and Spot Blood Oxygen Saturation

The spot SpO₂ levels and change from baseline (day 1) will be listed and summarized by treatment group and time point. The number and percentage of participants with SpO₂ levels

as per [Table 8] at any time point will be summarized by treatment group. The lowest SpO₂ level across the time points will be used in the analysis.

Table 8 Criteria for Assessing Spot Blood Oxygen Saturation

Parameter	Criteria
SpO ₂ level (%)	< 90, < 92, < 94, < 96

SpO₂: blood oxygen saturation

The number and percentage of participants who reach an alarm value of continuous pulse oximetry, and the number of times an alarm value was reached will be listed and summarized by treatment.

9.4.3.5 Electrocardiogram

9.4.3.5.1 12-lead Electrocardiogram

The number and percentage of participants with 12-lead ECG criteria as per [Table 9] will be provided by treatment group, at each time point and overall by visit.

The average of the triplicate ECG measurements will be used for the analysis.

Table 9 Criteria for 12-lead Electrocardiogram

Parameter	Criteria
Absolute QTcF Interval (msec)	> 450, > 480, > 500
PR (msec)	> 200
QRS (msec)	> 110
Heart Rate (bpm)	> 100
QTcF Interval Increases from Baseline (msec)	> 30, > 60

QTcF: corrected QT interval using Fridericia's formula

12-lead ECG data and interpretations will be listed.

9.4.3.6 Columbia-Suicide Severity Rating Scale

The listings will include only C-SSRS assessments that show at least 1 event of suicidality (suicidal ideation and/or suicidal behavior).

9.4.3.7 49-item Short Form of Addiction Research Center Inventory Scale

From the completed ARCI-49 questionnaire, scores for the amphetamine, benzedrine, pentobarbital-chlorpromazine-alcohol, morphine-benzedrine and lysergic-acid-diethylamide groups will be calculated. The calculated subscale score and change from baseline will be listed and summarized by treatment group and time point.

The algorithm for scoring the ARCI-49 [Martin et al, 1971] is presented in [Section 10.9 Appendix 9 49-item Short Form of Addiction Research Center Inventory Scale, Questionnaire Scoring]. One point will be given for each response that agrees with the scoring direction. Specifically, 1 point will be given for each "true" response (i.e., item has associated scoring coefficient +1), and 1 point will be given for each "false" response in the

reverse-scored items (i.e., item has associated scoring coefficient -1). Each subscale score will be derived as the linear combination (sum) of mathematically-signed points among the relevant items, i.e., matched true/false responses. Some items belong to more than 1 subscale.

No missing data will be imputed.

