	8 hours	X	X	X			X	X	X
	12 hours	X	X	X		X	X		X
	16 hours	X	X						
11	24 hours postdose day 10	X	X	X	X		X		
	36 hours postdose day 10	X	X						
12	48 hours postdose day 10	X	X	X	X				
	60 hours postdose day 10	X							
13	72 hours postdose day 10	X		X	X				
14	96 hours postdose day 10	X		X	X				
15	120 hours postdose day 10	X		X	X				
16	144 hours postdose day 10	X		X	X	X			
ESV	5 to 9 days after the day 16 pharmacokinetic sample/ED/ET	X		X	X	X			

ARCI-49: 49-item short form of Addiction Research Center Inventory scale; CO₂: carbon dioxide; ECG: electrocardiogram; ED: early discontinuation; ESV: end-of-study visit; ET: early termination; SpO₂: blood oxygen saturation

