9.4 Statistical Analyses

9.4.1 General Considerations

In general, data will be summarized with descriptive statistics for continuous endpoints, and frequency and percentage for categorical endpoints, unless otherwise specified. Percentages by categories will be based on the number of participants with no missing data (i.e., will add up to 100%).

Baseline will be defined as the last nonmissing observation prior to first administration of IP, unless otherwise specified.

Demographics and baseline characteristics (age, sex, race, ethnicity, body weight, height and BMI) will be summarized by treatment group and overall for all randomized participants.

The number and percentage of participants who completed and discontinued treatment and reasons for treatment discontinuation will be presented for all randomized participants and for participants in the safety analysis set (SAF) by treatment group (ASP8062 alone, placebo alone, morphine in combination with ASP8062, morphine in combination with placebo) and overall. Similar tables for screening disposition, investigational period disposition and follow-up disposition will also be presented for all randomized participants by treatment group (ASP8062 alone, placebo alone, morphine in combination with ASP8062, morphine in combination with placebo) and overall. All disposition details and dates of first and last evaluations for each participant will be listed.

Previous and concomitant treatment (medication and nonmedication therapy) and medical history will be listed. The number and percentage of participants exposed to IP will be summarized by treatment group (ASP8062 alone, placebo alone, morphine in combination with ASP8062, morphine in combination with placebo) and visit. All IP exposure data will be listed.

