2.	I am not as active as usual.	1				
3.	I have a feeling of just dragging along rather than coasting.	1				
4.	I feel sluggish.	1				
5.	My head feels heavy.	1				
6.	I feel like avoiding people although I usually do not feel this way.	1				
7.	I feel dizzy.	1				
8.	It seems harder than usual to move around.	1				
9.	I am moody.	1				
10.	People might say I am a little dull today.	1	-1			
11.	I feel drowsy.	1		-1		
12.	I am full of energy.	-1				
13.	Today I say things in the easiest possible way.				1	
14.	Things around me seem more pleasing than usual.				1	
15.	I have a pleasant feeling in my stomach.				1	
16.	I feel I will lose the contentment that I have now.				1	
17.	I feel in complete harmony with the world and those about me.				1	
18.	I can completely appreciate what others are saying when I am in this mood.				1	
19.	I would be happy all the time if I felt as I feel now.				1	
20.	I feel so good that I know other people can tell it.				1	
21.	I feel as if something pleasant has just happened to me.				1	
22.	I would be happy all the time if I felt as I do now.			-1	1	
23.	I feel more clear-headed than dreamy.	-1	1		1	
24.	I feel as if I would be more popular with people today.				1	1

#	Question	GROUP				
		PCA	B	LSD	MB	AMP
25.	I feel a very pleasant emptiness.				1	1
26.	My thoughts come more easily than usual.		1		1	1
27.	I feel less discouraged than usual.				1	1
28.	I am in the mood to talk about the feelings I have.		1		1	
29.	I feel more excited than dreamy.	-1				1
30.	Answering these questions was very easy today.		1			1
31.	My memory seems sharper to me than usual.		1			1
32.	I feel as if I could write for hours.		1			1
33.	I feel very patient.			-1		1
34.	Some parts of my body are tingling.		1	1		1
35.	I have a weird feeling.			1		1
36.	My movements seem faster than usual.		1			
37.	I have better control over myself than usual.		1			
38.	My movements seem slower than usual.		-1			
39.	I find it hard to keep my mind on a task or job.		-1			
40.	I don't feel like reading anything right now.		-1			
41.	It seems I am spending longer than I should on each of these questions.			1		
42.	My hand feels clumsy.			1		
43.	I notice my hand shakes when I write.			1		
44.	I have a disturbance in my stomach.			1		
45.	I have an increasing awareness of bodily sensations.			1		
46.	I feel anxious and upset.			1		
47.	I have unusual weakness of my muscles.			1		
48.	A thrill has gone through me one or more times since I started this test.	-1		1		

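### Does the wording of Section 9.4.3.7 reverse the reverse-keyed ARCI-49 items twice?

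*Combined protocol and SAP*

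**What the plan says.** Section 9.4.3.7 builds the score in steps. The general rule is: "One point will be given for each response that agrees with the scoring direction". The next sentence applies it in both directions. *True* earns 1 point on items with coefficient +1, and *false* earns 1 point on "reverse-scored items (i.e., item has associated scoring coefficient -1". The sentence in question follows: "Each subscale score will be derived as the linear combination (sum) of mathematically-signed points among the relevant items, i.e., matched true/false responses". The section notes that an item may belong to several subscales and closes with "No missing data will be imputed".

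Appendix 9 (Section 10.9) gives the key as a table of +1 and -1 entries for PCA, B, LSD, MB and AMP. For example, item 10, "People might say I am a little dull today", is +1 on PCA and -1 on B.

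On reporting, Section 9.4.3.7 says: "The calculated subscale score and change from baseline will be listed and summarized by treatment group and time point". Section 9.4.1 sets the reference: "Baseline will be defined as the last nonmissing observation prior to first administration of IP, unless otherwise specified". Table 3 lists the ARCI-49 as exploratory, and Section 9.1 states no hypotheses.

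**The concern.** A count of matches contains no negative points, so it is fair to ask what signs the third sentence means. The only signs in the documents are the coefficients in Appendix 9, and the preceding sentence has already used them to award a point for *false*. If they were applied again, a matched *false* would contribute -1 instead of +1 and the item would run in the wrong direction.

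That would matter for interpretation. PCA, the sedation-type subscale, is one of the three affected. If item 12 (feeling full of energy, coefficient -1) moved from *true* to *false* and nothing else changed, PCA should rise by 1, but the double reversal would make it fall by 1. Section 7.3.6 names sedation and somnolence as events of special interest for morphine, so the direction of a PCA change has meaning even in a descriptive table.

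The section also does not say what happens to a subscale when one of its items is unanswered.

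**Working it through.** The documents give no subscale range or worked example, so there is no stated figure to reproduce. The check uses the key in Appendix 9 and the schedule in Table 2.

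**Key (+1 / -1 entries).** PCA 11/4, B 9/4, LSD 10/4, MB 16/0, AMP 11/0, which is 15 + 13 + 14 + 16 + 11 = 69 entries. The 12 reverse entries are:
- PCA: items 12, 23, 29, 48
- B: items 10, 38, 39, 40
- LSD: items 11, 22, 33, 49

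**Three readings.** For one subscale, let p be the number of +1 items answered *true*, f the number of reverse items answered *false*, and t the number of reverse items answered *true*.
- (a) Match count: p + f
- (b) Coefficient applied to points already awarded: p - f
- (c) Coefficient applied to *true* answers: p - t

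Hence (a) - (b) = 2f, and (a) - (c) = f + t, the number of reverse items answered.

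| | PCA | B | LSD |
|---|---|---|---|
| Range under (a) | 0 to 15 | 0 to 13 | 0 to 14 |
| Range under (b) | -4 to 11 | -4 to 9 | -4 to 10 |
| All responses as keyed, (a) | 15 | 13 | 14 |
| All responses as keyed, (b) | 7 | 5 | 6 |
| All responses as keyed, (c) | 11 | 9 | 10 |

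MB (0 to 16) and AMP (0 to 11) are the same under all three readings.

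**Effect on change from baseline, complete questionnaires.** Under (b) the error is twice the change in f: 0 if no reverse item moves, and 2 x 4 = 8 if all four move the same way. Constructed example: all B items are *false* at baseline, then only item 38 moves to *true*.
- (a) 4 to 3, change -1
- (b) -4 to -3, change +1
- (c) 0 to -1, change -1

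Reading (c) differs from (a) by a constant 4, so its change scores are correct.

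**Blank items.** Reading (c) gives the same change as (a) whenever the number of reverse items answered is equal at both visits. If item 40 is blank at both and item 38 moves from *false* to *true*, both give -1. If item 40 is blank only at the later visit and nothing else changes, (a) goes from 4 to 3 and (c) stays at 0, a difference of 1.

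**How many values are involved.** Table 2 schedules 1 (day 1 predose) + 5 (day 9) + 5 (day 10) + 1 (day 11, "24 hours postdose day 10") = 12 administrations. With day 1 predose as baseline there are 11 changes per subscale, so 11 x 3 = 33 of 11 x 5 = 55 change values per participant fall on PCA, B and LSD. This counts values that could be touched. Under (b) a value is wrong only if its reverse items show a net move.

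**Which reading the text supports.** The points the section defines all equal 1, in both directions. A sum of them is reading (a). The disputed sentence explains its linear combination as a sum and its signed points as matched responses. No sentence says to multiply an awarded point by its coefficient.

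**The case for a change.** The strongest opposing case is that the explanation and the contradictory phrase share a sentence, so the text does not cancel its own ambiguity, and no range or worked example would expose a programming error. In addition, 7 of the 12 reverse-keyed items (10, 11, 22, 23, 29, 33, 48) are +1 on one subscale and -1 on another. A programmer therefore cannot flag an item as reversed once; the key has to be applied per item and subscale.

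Part of this stands. The phrase is poor drafting, and the per-subscale key needs care. But Appendix 9 already gives the key per subscale, and two explicit sentences define the point. Reading (b) requires an operation that the text does not state. The possibility of a programming error is a matter for program validation and does not show that the plan specifies the wrong score.

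On blank items, points are given per response, so an unanswered item earns none, imputation is excluded, and the section scores completed questionnaires. Whether a subscale with a blank is then reported or set to missing remains open. That detail is normally fixed in the programming specification.

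**Conclusion.** This is a clerical slip in wording, together with a small gap that analysts can fill; the plan need not change. Read as a whole, Section 9.4.3.7 prescribes the plain match count, and following it gives the correct score. The 2-points-per-item error, up to 8 points on PCA, B or LSD, arises only if a programmer adds a multiplication that the section does not ask for. Even then it would be confined to an exploratory scale that is listed and summarized without testing. No primary or secondary endpoint is touched.

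The conclusion rests on two things. The first is that the columns of the Appendix 9 table are read correctly; both the four-per-subscale split and the ranges depend on this. The second is that *matched responses* in the disputed sentence carries its ordinary meaning. The examples are constructed, since the documents give no response data.
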